2. LIST OF ABBREVIATIONS

See Medicine Glossary:

<http://glossary>

Term	Definition / description
ADS plan	Analysis data set plan
ALT	Alanine transaminase
AST	Aspartate transaminase
AUC _{0-∞}	Area under the concentration-time curve of the analyte in plasma over the time interval from 0 extrapolated to infinity
BMI	Body mass index
CARE	Clinical data Analysis and Reporting Environment
CI	Confidence interval
C _{max}	Maximum measured concentration of the analyte in plasma
CV	Arithmetic coefficient of variation
ECGPCS	ECG Pharmacokinetic Concentration Set
EDMS	Electronic documentation management system
gCV	Geometric coefficient of variation
gMean	Geometric mean
λ _z	Terminal rate constant of the analyte in plasma
Max	Maximum
MedDRA	Medical Dictionary for Regulatory Activities
Min	Minimum
N	Number of non-missing observations
P10	10th percentile
P90	90th percentile
PDS	Pharmacodynamic parameter analysis set
PKS	Pharmacokinetic parameter analysis set
PT	Preferred term
Q1	1st quartile
Q3	3rd quartile
RAGe	Report Appendix Generator system
REP	Residual effect period

Term	Definition / description
RPM	Report planning meeting
SD	Standard deviation
SOC	System organ class
TMF	Trial master file
TS	Treated set
ULN	Upper limit of normal
WHO-DD	World Health Organization Drug Dictionary

3. INTRODUCTION

As per ICH E9 (1) the purpose of this document is to provide a more technical and detailed elaboration of the principal features of the analysis described in the protocol, and to include detailed procedures for executing the statistical analysis of the primary and secondary variables and other data.

This Trial statistical analysis plan (TSAP) assumes familiarity with the Clinical Trial Protocol (CTP), including Protocol Amendments. In particular, the TSAP is based on the planned analysis specification as written in CTP Section 7 “Statistical Methods and Determination of Sample Size”. Therefore, TSAP readers may consult the CTP for more background information on the study, e.g., on study objectives, study design and population, treatments, definition of measurements and variables, planning of sample size, randomisation.

Study data (including data entered in the RAVE EDC system and external data provided by suppliers) will be stored in a Clinical Data Repository (CDR).

Pharmacokinetic (PK) parameters will be calculated using Phoenix WinNonlin™ software (version 6.3 or higher, [REDACTED]).

The statistical analyses will be performed within the validated working environment CARE, including SAS™ (current Version 9.4, by [REDACTED]), and a number of SAS™-based tools (e.g., macros for the analyses of AE data or laboratory data; Report Appendix Generator system (RAGe) for compilation/formatting of the CTR appendices).

4. CHANGES IN THE PLANNED ANALYSIS OF THE STUDY

All analyses as planned in the CTP will be performed and are described in more detail in this TSAP.

5. ENDPOINTS

5.1 PRIMARY ENDPOINT

Section 2.1.2 of the CTP:

The primary endpoint for assessment of safety and tolerability of BI 474121 is the percentage (%) of subjects with drug-related adverse events.

5.2 SECONDARY ENDPOINTS

5.2.1 Key secondary endpoints

[figure not shown]
This section is not applicable as no key secondary endpoints have been defined in the CTP.

[figure not shown]
5.2.2 Secondary endpoints

[figure not shown]
Section 2.1.3 of the CTP:

The following pharmacokinetic parameters will be determined if feasible:

- *AUC_{0-∞} (area under the concentration-time curve of the analyte in plasma over the time interval from 0 extrapolated to infinity)*
- *C_{max} (maximum measured concentration of the analyte in plasma)*

6. GENERAL ANALYSIS DEFINITIONS

6.1 TREATMENTS

For basic study information on investigational products, assignment to treatment groups and selection of doses, please see CTP Sections 3 and 4.

It is planned that 32 healthy Japanese male subjects participate in this randomized, double-blind, placebo-controlled study. The subjects will be assigned to one of 4 dose groups consisting of 8 subjects per group, and will be randomized to placebo or active treatment within their dose group. Within each dose group, 6 subjects will receive a single dose of active drug and 2 subjects will receive a single dose of placebo.

Table 6.1: 1 Treatments and labels used in the analysis

Treatment	Label in dataset	Short label
P	Placebo#	Placebo
A	BI 474121, tablet, 2.5 mg, po, qd	BI 2.5mg
B	BI 474121, tablet, 2*2.5 mg, po, qd	BI 5mg
C	BI 474121, tablet, 10 mg, po, qd	BI 10mg
D	BI 474121, tablet, 2*10 mg, po, qd	BI 20mg

#For data analysis purposes, the placebo group will consist of all subjects treated with placebo, regardless of the dose group in which they were treated.

Section 1.2.7 of CTP:

The Residual Effect Period (REP) of BI 474121, when measurable drug levels and/or pharmacodynamic effects are still likely to be present, is not known. Conservatively (...) a REP of 7 days is assumed, i.e. the individual subject's end of trial is on Day 8-15 following dosing with investigational drug.

The following study phases will be defined for the analysis of AEs:

- **Screening** (ranging from 0:00h on day of informed consent until first administration of study medication)
- **On treatment** (ranging from the time of first administration of study medication (BI or Placebo) until 168 hours (7 days) after time of administration)
 - ➔ Labelled Placebo, BI 2.5mg, BI 5mg, BI 10mg, BI 20mg
- **Follow-up (F/U)** (ranging from 168 hours (7 days) after administration of BI or Placebo until 0:00 h on the day after trial termination date)
 - ➔ Labelled F/U

Section 7.3.4 of the CTP: *Note that AEs occurring after the last per protocol contact but entered before final database lock will be reported to Pharmacovigilance only and will not be captured in the trial database.*

Displays of AEs will be stratified by dose group as specified in [Table 6.1: 1](#). The following AE displays will be provided in the report:

Section 15.3 and Appendix 16.1.13.1.8 (for ClinicalTrials.gov) of the CTR displays:

In these displays, the on treatment phase will be analysed (labelled with the name of the study treatment (short label)). Screening and follow-up phases will not be included in this analysis. The following totals will be provided in addition (for 15.3 only, except for ECG):

- a total over all BI on treatment phases (“**BI Total**”),
- a total over all on treatment phases included in this analysis (“**Total**”).

In Section 15.4 and Appendix 16.2 (Listings) of the CTR displays, screening and follow-up periods will be included and no totals will be provided.

For detailed information on the handling of the treatments refer to Technical TSAP ADS (analysis data set) plan and Analysis Data Reviewers guide.

6.2 **IMPORTANT PROTOCOL DEVIATIONS**

Data discrepancies and deviations from the CTP will be identified for all treated subjects.

Consistency check listings (for identification of deviations of time windows) and a list of protocol deviations (e.g. deviations in drug administration, in blood sampling times, etc.) will be provided to be discussed at the Report Planning Meeting (RPM). At this meeting, all manual deviations identified at the sites by the CRAs and deviations too complex to program will be reviewed by the trial team to decide which are considered important. For definition of important protocol deviations (iPD), and for the process of identification of these, refer to the Boehringer Ingelheim (BI) SOP "Identify and Manage Important Protocol Deviations (iPD)" ([2](#)).

Section 7.3 of the CTP: *Important protocol deviation (iPD) categories will be specified in the iPD specification file prior to trial initiation. IPDs will be identified no later than in the Report Planning Meeting, and the iPD categories will be updated as needed.*

If any iPDs are identified, they are to be summarised into categories and will be captured in the iPD specification file (i.e. the DV domain specifications) and the decision log. Handling of iPDs in the analysis is included in the DV domain specifications and stored within the TMF in EDMS.

The iPDs will be summarized and listed in the CTR.

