#### **7.3.4 Safety analyses**

Safety will be assessed as defined by the endpoints listed in Section [2.1.2](#) and [2.2.2](#) based on the TS. Safety analyses will be descriptive in nature and will be based on BI standards.

For all analyses the treatment actually administered (= treatment at onset) to the subject will be used (any deviations from the randomised treatment will be discussed in the minutes of the Report Planning Meeting).

Treatments will be compared in a descriptive way. The placebo group in the safety evaluation will consist of all subjects treated with placebo, regardless of the dose group in which they were treated. The test treatment groups will be compared to the placebo group in a descriptive way. Tabulations of frequencies/proportions will be used for the evaluation of categorical (qualitative) data, and tabulations of descriptive statistics will be used to analyze continuous (quantitative) data.

Measurements (such as ECGs, vital signs, or laboratory parameters) or AEs will be assigned to treatments (see Section [4.1](#)) based on the actual treatment at the planned time of the

Proprietary confidential information © 2021 Boehringer Ingelheim International GmbH or one or more of its affiliated companies

measurement or on the recorded time of AE onset (concept of treatment-emergent AEs). Therefore, measurements planned or AEs recorded prior to intake of the trial medication will be assigned to the screening period, those between the trial medication intake and end of REP (see Section [1.2.7](#)) will be assigned to the treatment period. Events occurring after the REP but prior to trial termination date will be assigned to 'follow-up'. These assignments including the corresponding time intervals will be defined in detail in the TSAP. Note that AEs occurring after the last per protocol contact but entered before database lock will be reported to Pharmacovigilance only and will not be captured in the trial database.

Additionally, further treatment intervals (called analysing treatments) may be defined in the TSAP in order to provide summary statistics for other than the above periods, such as combined treatments, on-treatment totals, or periods without treatment effects (such as screening and post-study intervals).

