7.4 PRIMARY ENDPOINT

Refer to TSAP [Section 7.8](#) for a description of the analysis of the primary endpoint.

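### Does the 168-hour adverse-event window wrongly leave end-of-trial findings out of the primary endpoint?

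*SAP*

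**What the plan says.** Protocol 2.1.2 words the primary endpoint without a time limit. SAP 7.4 refers the reader to SAP 7.8 "for a description of the analysis of the primary endpoint", and SAP 7.8.1 assigns every AE to one of the phases defined in SAP 6.1.

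- **On treatment:** from dosing "until 168 hours (7 days) after time of administration".
- **Follow-up:** "ranging from 168 hours (7 days) after administration of BI or Placebo until 0:00 h on the day after trial termination date".
- **Basis of the split:** the residual effect period (REP). SAP 6.1 says it is not known and conservatively assumes 7 days, so that a subject's "end of trial is on Day 8-15 following dosing with investigational drug".
- **CTR Section 15.3 and the ClinicalTrials.gov appendix:** on-treatment phase only. "Screening and follow-up phases will not be included in this analysis".
- **CTR Section 15.4 and Appendix 16.2:** "screening and follow-up periods will be included and no totals will be provided".

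The protocol sets the same rule. Section 7.3.4 assigns AEs to treatment by relying "on the recorded time of AE onset" and counts those between intake and the end of the REP as treatment period. It continues: "Events occurring after the REP but prior to trial termination date will be assigned to" follow-up. It leaves the exact intervals to the SAP, which may define further ones.

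**The concern.** Read in sequence, these sections put the last scheduled examination at or after the point where the primary endpoint stops counting. Some checks have their only planned post-dose assessment at that visit: fibrinogen, ALP, GGT, lipase, albumin and uric acid (Protocol 5.2.4), and the physical examination and body temperature (Flow Chart notes and Protocol 5.2.1). The other safety laboratory tests have no planned sample between 72 h and that visit. A symptom can be recalled and dated back; an abnormal laboratory value usually cannot. If its onset is dated to the visit, a finding judged drug-related would not enter the percentage, and the endpoint's wording in Protocol 2.1.2 does not warn the reader of this.

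At stake would be a primary safety percentage that is too low by design, in groups where one subject moves the figure visibly.

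**Working it through.** **1. The window.** Inputs: REP of 7 days (SAP 6.1) and dosing at about 08:00 on Day 1 (Flow Chart).

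- 7 × 24 = 168 h, which reproduces the SAP's figure.
- Day 1 08:00 + 168 h = Day 8 08:00.
- A visit at 08:00 on Day 8 is at 7 × 24 = 168 h; on Day 15 it is at 14 × 24 = 336 h.
- Day 9 begins at 184 h, so 7 of the 8 permitted visit days lie wholly outside the window. Day 8 is inside only before the dosing clock time (160 to 168 h).

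The dates behind the concern are therefore right.

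**2. The rule against the protocol.** Protocol 7.3.4: intake to end of REP is treatment, and later is follow-up. SAP 6.1: dosing to 168 h is on treatment, and later is follow-up. With a 7-day REP these are the same rule. The visit opens on Day 8 because the REP ends then, so its position after the window follows from the design. Phase also depends on recorded onset and not on detection: an event first reported at the visit but starting before 168 h is counted.

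**3. The length of the window.** Input: half-life of about 20 h (Protocol 1.4.3).

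- 168 / 20 = 8.4 half-lives.
- 0.5^8.4 = 0.003, so about 0.3% would remain under simple one-rate elimination.
- The 336 h point is 336 / 20 = 16.8 half-lives.

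**4. Where later information is reported.**

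| Information after 168 h | Where it is reported |
|---|---|
| AEs starting in follow-up | CTR Section 15.4 and Appendix 16.2 (SAP 6.1) |
| SAEs, AESIs, other significant AEs | Listed separately (Protocol 7.3.4) |
| Laboratory values | Statistics and change from baseline by planned time point, using the subject's worst value; out-of-range values flagged (SAP 7.8.2) |
| Blood pressure and pulse rate | Statistics and change from baseline by planned time point (SAP 7.8.3) |
| Body temperature | Listed (SAP 7.8.3) |

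SAP 6.1 introduces its phases for the analysis of AEs. Nothing in the visible text removes the end-of-trial visit from the laboratory or vital-sign tables. A shift in ALP or lipase at that visit would be tabulated by treatment as a measurement, although not counted as an AE.

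**5. The size of one event.** Denominators: 6 per dose, 4 × 2 = 8 on pooled placebo, 4 × 6 = 24 on active drug.

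| Group | One subject | Exact 95% CI with no event | Exact 95% CI with one event |
|---|---|---|---|
| Dose group, n = 6 | 1/6 = 16.7% | 0 to 45.9% | 0.4 to 64.1% |
| Placebo, n = 8 | 1/8 = 12.5% | 0 to 36.9% | 0.3 to 52.7% |
| All active, n = 24 | 1/24 = 4.2% | 0 to 14.2% | 0.1 to 21.1% |

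These figures describe any single event at any time; they are no evidence about late ones. The documents give no rate for late drug-related events. Under assumed rates per active subject of 0.5%, 1%, 2% and 5%, the chance of at least one among 24 is 1 − (1 − p)^24 = 11%, 21%, 38% and 71%. The spread shows that the answer depends wholly on the assumption.

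**6. The boundary at exactly 168 h.** SAP 6.1 uses the same wording at time zero: screening runs up to first administration and the on-treatment phase starts with it. There the boundary moment belongs to the later phase. Read the same way, an onset at exactly 168 h is follow-up.

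**The case for a change.** The strongest counter-argument concerns findings without a recallable onset. The 7-day REP is an assumption and the SAP says the true value is not known. The investigator's causality judgement already weighs time to onset (Protocol 5.2.6.1.6), so a late event still called drug-related has passed that filter. AEs are collected to the individual end of trial (Protocol 5.2.6.2.1), so the data will exist, and Protocol 7.3.4 allows an extra interval.

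Part of this stands. No frequency table for follow-up AEs is described, and the visible text does not say whether Section 15.4 holds counts or only listings. Clinically relevant findings on physical examination or on the locally read end-of-trial ECG would appear as AEs, without a summary table by time point.

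It does not amount to a fault. To alter the percentage, an event must start after 168 h, be judged clinically relevant if it is a laboratory, ECG or examination finding, be judged drug-related, and occur in a subject with no earlier drug-related AE. An implausible time to onset counts against causality, which thins that group further. A fixed window also gives every subject who completes follow-up the same observation time. A table running to trial termination would mix about 168 to 336 h and admit late background events. On dating, AE records must include the time of onset (Protocol 5.2.6.2.1), and SAP 6.6 refers missing or incomplete dates to a cited standard that is not available here.

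**Conclusion.** The concern does not hold. An AE dated to the end-of-trial visit normally stays outside the primary percentage, but this is the treatment-emergent rule the protocol prespecifies, and the SAP applies it without deviation. The two documents agree, and the window covers 8.4 half-lives. Followed as written, the plan gives a sound descriptive result, and later events remain reported elsewhere. An additional table over the whole observation period would be a matter of preference: it would leave the primary percentage and every other planned result unchanged.

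This rests on the half-life of about 20 h taken from the first-in-human study, on the 7-day REP being as conservative as the SAP states, and on the end-of-trial visit being included in the laboratory and vital-sign summaries by planned time point, which is the natural reading of SAP 7.8.2 and 7.8.3. The number of late drug-related events to expect cannot be derived from the documents.

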6.3 SUBJECT SETS ANALYSED

Section 7.3 of the CTP:

- *Treated set (TS): The treated set includes all subjects who were randomized and treated with at least one dose of study drug. The treatment assignment will be determined based on the first treatment the subjects received. The treated set will be used for safety analyses.*
- *Pharmacokinetic parameter analysis set (PKS): This set includes all subjects in the TS who provide at least one PK endpoint that was not excluded due to a protocol violation relevant to the evaluation of PK or due to PK non-evaluability (as specified in the following subsection 'Pharmacokinetics'). Thus, a subject will be included in the PKS, even if he/she contributes only one PK parameter value for one period to the statistical assessment. Descriptive and model based analyses of PK parameters will be based on the PKS.*
- *Pharmacodynamic parameter analysis set (PDS): This set includes all placebo subjects and all subjects included in the PKS.*

(...)

Pharmacokinetics

(...)

Plasma and urine concentration data and parameters of a subject will be included in the statistical PK analyses, if they are not flagged for exclusion due to a protocol violation relevant to the evaluation of PK (to be decided no later than in the Report Planning Meeting) or due to PK non-evaluability (as revealed during data analysis, based on the criteria specified below). Exclusion of a subject's data will be documented in the CTR.

Relevant protocol violations may be

- *Incorrect trial medication taken, i.e. the subject received at least one dose of trial medication the subject was not assigned to*
- *Incorrect dose of trial medication taken*
- *Use of restricted medications*

Plasma and urine concentrations and/or parameters of a subject will be considered as non-evaluable, if for example

- *The subject experienced emesis that occurred at or before two times median t_{max} of the respective treatment (Median t_{max} is to be determined excluding the subjects experiencing emesis),*
- *Missing samples/concentration data at important phases of PK disposition curve.*

All ECG analyses are performed on the TS, except for the exposure-response analyses, which are performed on the ECGPCS defined below.

ECG Pharmacokinetic Concentration Set (ECGPCS): This subject set includes all subjects from the TS who provide at least one pair of a valid drug plasma concentration and a corresponding (i.e. time-matched) ECG endpoint to be used in the exposure-response analyses. For placebo subjects, the plasma concentration is set to zero and hence always considered as valid. The decision whether a time deviation between PK blood sampling and ECG recording is acceptable (and thus whether the pair of values will be used) is to be made no later than at the RPM before data base lock. For subjects treated with active drug, the decision about concentration value validity needs to be made within the Clinical Pharmacology Group.

Table 6.3: 1 Subject sets analysed

Class of endpoint	Subject analysis set			
	TS	PKS	PDS	ECGPCS
Primary endpoint and further safety assessments (incl. ECG)	X			
Analyses of PK endpoints		X		
Analyses of PD/biomarker endpoints			X	
ECG exposure response analysis				X
Demographic/baseline parameters	X			
Important protocol deviations	X			
Disposition	X			
Exposure	X			

6.5 POOLING OF CENTRES

This section is not applicable, because the study was performed in only one centre.

6.6 HANDLING OF MISSING DATA AND OUTLIERS

Handling of missing data and outliers will be performed as described in the CTP, Section 7.5. Missing or incomplete AE dates are imputed according to BI standards (see BI-KMED-BDS-HTG-0035) (3).

Missing data and outliers of PK data are handled according to BI standards (see BI-KMED-TMCP-MAN-0012 (4) and BI-KMED-TMCP-MAN-0014 (5)).

If single cardiac cycles of an ECG (out of the generally four) are missing, the arithmetic mean for this single ECG will be computed with the reduced (1, 2 or 3) number of cardiac cycles.

If replicate ECG recordings are missing, the arithmetic means per time point will be computed with the reduced number (1 or 2) of recordings.

For the classification of the on-treatment QTc/QT intervals into “no new onset” / “new onset” categories, the handling of missing value is described in Additional [Section 10.1.3](#).

For subjects on active drug (e.g. post dose time points), missing plasma concentration values with ‘BLQ’ in the comment field will be replaced by $\frac{1}{2}$ LLOQ for the exposure-response analysis. For placebo subjects, the missing plasma concentration values will be replaced by 0 for the exposure-response analyses.

6.7 BASELINE, TIME WINDOWS AND CALCULATED VISITS

The baseline value is defined as the last measurement before administration of trial medication (BI 474121 or Placebo).

Section 6.1 of the CTP: *Exact times of measurements outside the permitted time windows will be documented. The acceptable time windows for screening and the end of trial examination are provided in the CTP Flow Chart.*

Study measurements and assessments scheduled to occur ‘before’ trial medication administration on Day 1 are to be performed and completed within a 3 h-period prior to the trial drug administration (including blank values for PK and biomarkers).

The acceptable deviation from the scheduled time for vital signs, ECG, start of first RR measurement in orthostatic tests, and laboratory tests will be ± 15 min for the first 4 h after trial drug administration, ± 30 min thereafter on Day 1, ± 60 min on Day 2, and ± 120 min from 48 h post administration onwards.

Starting from 48 h post administration, a deviation from the scheduled time for PK and biomarker sampling as well as for AE questioning of ± 120 min is acceptable.

Adherence to time windows will be checked via the consistency check listings at the RPM.

Unscheduled measurements of laboratory data, orthostatic testing and vital signs data will be assumed to be repeat measurements of the most recent scheduled measurement (e.g. for follow-up or confirmation of a particular value). Therefore, unscheduled measurements will be assigned to the planned time point of the previous scheduled measurement.

There will be a centralised evaluation of the 12-lead ECG recordings at the time points and for the ECG recordings specified in [Table 6.7: 1](#):

Table 6.7: 1 Time schedule of 12-lead ECG recordings

Visit	Day	Planned time [hh:mm] (relative to drug administration)	Study phase	Central evaluation
1	-28 to -1		Screening	NA
2	1	-01:00	Baseline	First ECG of each of the 3 triplicate baselines
		-00:45		
		-00:30		
		00:30		
		01:00		
		01:30		
		02:00		
		03:00		
		04:00		
		06:00		
		08:00		
		12:00		
	2	24:00		
		34:00		
	3	48:00		
	4	72:00		Single ECG
	5	96:00		Single ECG
3	8 to 15		End of trial examination	NA

At Visits 1 and 3 (screening and end of trial examination), single ECGs will be recorded and will not be transferred to the central ECG lab. Three triplicate ECGs will be recorded as the baseline before drug administration, but only the first ECG of each of the 3 baseline triplicates will be transferred to the database. At all other time points (except for ECGs on day 4 and 5 of Visit 2), 1 triplicate ECG will be recorded, but only the first single ECG of the triplicate will be transferred to the database. The baseline value of an ECG variable is defined as the mean of the ECG variable values prior to drug administration.

For the exposure response analyses, pairs of ECG variables and corresponding plasma concentrations will be built using the same planned time points, e.g., the HR change from baseline and the plasma concentration measured at planned time 0:30 will build one pair. Whether a time deviation between PK blood sampling time and corresponding ECG recording is too big and the pair has to be excluded from the analysis will be decided no later than at the RPM. Data exclusion due to time deviations will only be applied to subjects on active study treatment.

In line with the tolerated time deviations of previous trials in this project, the acceptable maximum time deviations between ECG recordings and plasma concentration sampling are proposed to be

- 10 minutes for up to 1 hours (including) after dosing,
- 20 minutes for time points from more than 1 hour to 12 hours after dosing, and
- 60 minutes for time points at 12 hours or later after dosing,

Pairs with time deviations exceeding those specified above will be excluded from exposure-response analyses. When the sampling time of the blood sample or the ECG recording is not available, the pair will also be excluded.

As the clinical trial protocol permits larger time deviations of ECG measurements from the planned time in the flow chart, and consequently indirectly accepts larger time deviations of ECG and PK sampling, a sensitivity analysis will be done. For the sensitivity analysis, the acceptable maximum time deviation between ECG recording and plasma concentration sampling are proposed to be

- 15 minutes for up to 4 hours (including) after dosing,
- 30 minutes for time points from more than 4h to 24h after dosing,
- 60 minutes for time points at 24h to 48h after dosing,
- 120 minutes for time points at 48 hours or later after dosing.

